1) "How do I feel today?" – This component of the app allows participants to fill in a questionnaire every day to report their current situation with respect to 22 side effects that are commonly experienced during therapies for lung cancer and were identified from the literature. Symptoms will be rated on a scale from 0 to 4 (where 0 is symptom not present, 4 is maximum degree of severity). Questions were adapted for patient use from the National Cancer Institute's Common Terminology Criteria for Adverse Events (CTCAE) (final list is available as an attachment "4.2_LuCApp_Annex 2_Adverse event list") (17). LuCApp will trigger alerts to healthcare professionals whenever a symptom of level 3 or above is inserted. Although the compilation is possible multiple times per day at will, patients will receive a reminder (as a mobile banner or email) to fill in this questionnaire every three days. Up to three different reminders will be sent at noon, 6 p.m. and 9 p.m. to encourage patients to self-report their symptoms using a recall period of the past 24 hours. Symptom reports are available for clinicians only.

In order to identify this comprehensive list of symptoms, first, a rapid review of the literature was conducted. References considered included:

- a. The Edmonton Symptom Assessment System (ESAS): 9 most common symptoms in cancer patients (first 9 symptoms) (25);
- b. Symptoms identified from a systematic review of studies in adults with lung cancer (26), another review the common symptoms in advanced NSCLC (27), and a third review of symptoms at initial evaluation of lung cancer patient (28).

[figure not shown]
This activity resulted in a list of 68 symptoms. From this list, lung cancer specialists who are investigators in this trial checked those symptoms that they consider relevant for the patient population under investigation. A second team of experts was then asked whether those symptoms not selected by the experts but identified in the literature would also be worth including. These included: anorexia, weight loss (clinical parameter), constipation, weakness, insomnia, dry mouth, remembering, and peripheral neuropathy. A final list was then circulated and validated amongst all experts and is available as an attachment to this protocol.

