Figure 4 - An example of how trends for different symptoms and parameters are visualized in the app

- 6) “Info” – In this final section, in order to increase the overall awareness of the disease and its potential treatments, the most relevant educational material is collected. This section includes some general information on lung cancer, therapies, patients’ rights, up to a series of institutional useful links (such as nearest pharmacy, hospital contacts) that patients can browse if needed (Figure 5).

Figure 5 - An example of how information is visualized in the app

Continuity in the utilization of the application will be strongly recommended. Participants will be advised to access the App daily to receive their daily tip and enter their temperature information. Questionnaires and other clinical parameters will have to be entered according to the schedule, but additional information can be added at discretion and alerts will activate whenever necessary. Patients will be advised to enter their daily body temperature at similar times each day and to use the same scale to measure their weight. To facilitate a greater use of the application, LuCApp provides for several rounds of banner reminders (better detailed above) scheduled on days when the input of a specific information is due according to study protocol.

Patients in the standard of care will follow the routine procedures and will be assisted by a clinical team at their site. Such professionals will still provide frequent assistance related to the trial since they will administer questionnaires when due and will update the CRF for the standard of care patients. On the other hand, in order to deal with the intervention arm, healthcare professionals will be trained through dedicated sessions prior to the launch of the patient recruitment phase. Contact details of LuCApp developers and technicians will be provided for assistance. However, if the technology does not function properly and the clinician believes an action is urgently needed for a patient, the research team is advised that standard of care applies to the intervention arm, too. During weekends it is possible that clinicians will not be reachable or will not reply promptly to alerts. Also in this case patients are advised to use the standard of care approach (e.g. out-of-hours service doctor, emergency department). The clinical teams that will take care of the intervention patients will be different from the standard

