of care arm ones, to ensure that behaviors and results will not be influenced. The research teams are also advised not to share feedback or comments for the duration of the trial in order to reduce performance bias as much as possible. Clinicians will receive alerts on their dedicated LuCApp device and will be responsible for managing them in a timely way. A single alert will be generated for each patient and clinical parameter monitored (i.e. temperature, weight, side effects). Healthcare professionals will then be able to gain more information on the symptoms that triggered the alert and to monitor the longitudinal trend of side effects both on their device and on the LuCApp website from a PC or laptop. Professionals will be able to access all other patient information on the secure LuCApp website, only. In response to an alert triggered for a specific patient, clinicians will be requested to act within 24 hours and to document the type of intervention performed among a list of possible alternatives derived from the literature: referral to the ER/hospital, telephone counselling about symptom management, dose modification, supportive medication initiation/change, visit anticipation (13).

To guarantee a greater use of the application automated reminders will be sent to participants both via email and via push notification. Participants will be prompted, via an automated message to update their body temperature and their weight and to fill out the side effects questionnaires. Three rounds of alerts will be generated at 12, 6 and 9 p.m. on the dates when the input of the relative data is scheduled (daily for body temperature, weekly for weight and every three days for the side effects questionnaire, see above).

Both groups will have access to treatment as usual. However, additional training will be provided to intervention arm participants right after enrolment: LuCApp features will be better detailed and training sessions will be scheduled accordingly. Furthermore, during the trial, a support center (“helpdesk”) will be available to help participants with any technical issues that may occur.

Standard of care

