Usual care will consist of standard procedures currently available at participating centers for monitoring and documenting symptoms. These therapeutical procedures are based on the guidelines developed by the National Comprehensive Cancer Network (NCCN) and the Associazione Italiana di Oncologia Medica (AIOM) (20). Symptoms for control arm patients will be discussed and registered during scheduled clinical visits

with the oncologists. Standard-of-care patients will fill out their PROMs following the same schedule identified for LuCApp patients with paper questionnaires during clinic visits, or at home (having received paper questionnaires during the previous visit) or via telephonic interviews with the research team. Patients are usually allowed to contact their relative sites for concerning symptoms that occur between scheduled visits or advised to see the out-of-hour doctor or the emergency department if needed. This option is also recommended for the intervention arm during weekends.

Outcomes

As discussed above, the overarching research question of this study is to explore and pilot the impact of using LuCApp on relevant outcomes in patients with lung cancer. LuCApp has several functionalities and this pilot explores whether these functionalities impact on the patients' health-related quality of lives (HRQoL) and needs in cancer supportive care. It also aims to assess whether it improves the burden on caregivers and the satisfaction with the use of the app. Finally, the cost-effectiveness of LuCApp will be explored, based on the improvement in HRQoL and the resources being used to manage the disease throughout the study period.

A number of outcome measures have been identified to allow the assessment of the above trial objectives. LuCApp will be evaluated in terms of: (1) impact on HRQoL, (2) impact on cancer supportive care needs, (3) impact on the burden for caregivers, (4) resource use, (5) usability and satisfaction with LuCApp. The rationale for selecting these measures and their characteristics are summarized in the next sections.

(1) HRQoL

The impact on HRQoL of using LuCApp will be measured with existing valid and reliable patient-reported outcome measures (PROMs). Their selection was based on the availability of a validated Italian version, for self-report use, that can be administered both on paper and via smartphones or tablets, and commonly used in lung cancer patients.

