except that the wording of the items does not refer to a usability-testing situation but is rather appropriate for a field-testing situation. The CSUQ was later adapted for mobile apps usability testing to elicit participant satisfaction with the PAediatric Risk Assessment (PARA) app, a mHealth tool developed to help health care professionals in resource-limited settings detect patients at high risk of both in-hospital and post-discharge mortality (48). Based on this revised version, the questionnaire was further elaborated upon: the final version consists of 12 items evaluated on a Likert scale ranging from 1 (“Strongly agree”) to 7 (“Strongly Disagree”). In addition, three qualitative questions were added to draw further information on the application and on the generalizability of LuCApp in the current and other clinical contexts: 1) “What do you like the most about the App?”; 2) “What do you like the least about the App”; 3) “How could the App be changed to make it easier to use?”. No validated Italian version of the CSUQ was available, so the authors, in cooperation with healthcare professionals of the participating sites, developed the current version. The questionnaire will be administered at the end of the study.

(5) Resource use

The perspective taken for the evaluation of resource consumption will be that of the National Healthcare System. In order not to overload patients and the App design with additional modules, resource use will be captured through patients reports of symptoms and clinicians actions in response to those symptoms (e.g. prescriptions, hospitalization, change in therapy). Moreover, additional information will be obtained for both control and treatment group patients via a form administered by the physician during the clinics. Unitary costs will be expressed as euros 2018. Drug unitary costs will be derived from national price listings, laboratory and instrumental tests will be valued according to the outpatient procedures formulary in accordance with the ongoing policies of Lombardy Region as well as eventual hospitalizations.

Figure 6 summarizes the data collection process throughout the study.

Figure 6 - Time-points of outcomes assessment

Sample size

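### Resource use may be recorded more completely in the LuCApp arm than in controls, so the exploratory cost comparison can be biased, most likely against LuCApp

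*Combined protocol and SAP*

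**What the plan says.** Outcomes, (5) Resource use, names two sources. The first is that "resource use will be captured through patients reports of symptoms and clinicians actions in response to those symptoms"; the stated reason is to spare patients and the App further modules. The second is that "additional information will be obtained for both control and treatment group patients via a form administered by the physician during the clinics".

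In the LuCApp arm, the Intervention (LuCApp) section describes a continuous record between visits. Symptoms can be entered daily, and "patients will receive a reminder (as a mobile banner or email) to fill in this questionnaire every three days". Temperature and weight entries can also raise alerts. After an alert, "clinicians will be requested to act within 24 hours and to document the type of intervention performed among a list of possible alternatives"; the alternatives include hospital referral, telephone counselling, treatment changes and an earlier visit.

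For controls, the Standard of care section says: "Symptoms for control arm patients will be discussed and registered during scheduled clinical visits". It also says: "Patients are usually allowed to contact their relative sites for concerning symptoms that occur between scheduled visits". They may be directed to the out-of-hours doctor or emergency department as well. The Intervention section adds, of the clinical teams, that "they will administer questionnaires when due and will update the CRF for the standard of care patients". No log of control contacts between visits, or of the actions that follow them, is described.

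Statistical methods compares resource use and costs between the arms with parametric and non-parametric tests. It does not say which source feeds the comparison, how app and form records are merged, or whether results will be shown by source.

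**The concern.** A cost comparison is fair only if a contact of a given kind has the same chance of being recorded in each arm. Here one arm carries an extra, near real-time record of clinician actions, and the other depends on what is recalled and written down at the next visit. A telephone call, a medication change or an unscheduled visit could be captured in the LuCApp arm and missed in controls. A contact could also be counted twice in the LuCApp arm, once in the log and once on the form.

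The measured difference would then mix true use with completeness of recording, and no test applied afterwards can separate the two. The trial is not blinded, and different clinical teams look after each arm, so recording habits may differ too. At stake is the cost side of the cost-effectiveness question, which the protocol lists among its aims.

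**Working it through.** The plan gives no figure for this point, so there is nothing to reproduce. The check sets the sections side by side and then shows how unequal capture would act, on assumed rates.

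**What is described for each arm**

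| Source | LuCApp | Control |
|---|---|---|
| Repeated symptom reports between visits | Yes, reminder every 3 days | None described |
| Documented clinician actions | Yes, after each alert | None described |
| Symptoms registered at scheduled visits | Usual care applies | Yes |
| CRF updated by clinical team | eCRF fed by app entries | Yes; resource content not stated |
| Physician form at clinics | Yes | Yes |

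The EQ-5D-5L section spaces its questionnaire every 3 ± 1 weeks to follow visit intervals. If clinic visits keep that spacing, there are 14 to 28 days between them. With a reminder every 3 days, a LuCApp patient is prompted about 5 to 9 times between visits (14/3 = 4.7; 28/3 = 9.3). The control schedule described has no prompt in that interval.

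**Illustration in contacts**

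Assume equal true use. Let *f* be the share of contacts the form catches in either arm, and *a* the share the log catches in the LuCApp arm only. With duplicates removed, the observed ratio of contacts, LuCApp to control, is

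[*f* + (1 − *f*) × *a*] / *f*.

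- *f* = 0.90, *a* = 0.50: 0.95/0.90 = 1.06
- *f* = 0.80, *a* = 0.75: 0.95/0.80 = 1.19
- *f* = 0.70, *a* = 1.00: 1.00/0.70 = 1.43
- *f* = 1.00, any *a*: 1.00

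Varying *a* from 0.25 to 1.00 gives 1.03 to 1.11 at *f* = 0.90, 1.06 to 1.25 at *f* = 0.80, and 1.17 to 1.67 at *f* = 0.60.

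**Double counting.** If a share *d* of the contacts present in both sources is counted twice, add *f* × *a* × *d* to the numerator. With a complete form (*f* = 1.00) and *a* = 0.50, *d* = 0.10 gives 1.05 and *d* = 0.20 gives 1.10. A complete form is therefore not enough without a merging rule.

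**From contacts to cost.** If contacts seen only in the log cost on average *k* times those the form catches, the cost ratio is 1 + *k* × (contact ratio − 1), with duplicates removed. It equals the contact ratio only when *k* = 1. If the log-only contacts are mainly telephone calls, *k* is well below 1 and the cost ratio is nearer 1. The documents do not give *k*.

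**Direction.** The ratio can also fall below 1. If LuCApp physicians, having already documented an action, fill in the form less fully, so that it catches 0.70 in their arm against 0.90 in controls, and *a* = 0.50, the ratio is (0.70 + 0.30 × 0.50)/0.90 = 0.85/0.90 = 0.94.

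**The case against.** The strongest reply is that the plan never says that symptom reports and responding actions come from LuCApp alone. The Resource use text is general, its examples (prescriptions, admissions, therapy changes) apply to any patient, and controls have symptoms registered at visits and a CRF. Nor does it name the alert log as the cost source or say that log and form will be added together. This stands. A reader might infer that the plan assigns the first source to one arm, or makes the alert log its main source, but the documents do not state either. What they support is narrower: the only between-visit reports and action list described are those of the app, and nothing equivalent is described for controls.

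Second, the effect on cost may be small. Valuation sources are named for drugs, laboratory and instrumental tests and admissions, not for telephone advice, and the log records the type of action without quantities. This stands as well, and it is why the percentages above must not be read as cost estimates.

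Third, the content, recall period and frequency of the form are not in the text and may be in an attachment. A complete form would equalise capture, but it would still not supply a rule for merging records.

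Fourth, a form-only comparison could drop real health-service costs that alerts set off. That is a fair warning about the remedy. It is met only if the form asks about care between visits.

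Last, this is a feasibility trial and the cost-effectiveness work is exploratory. That limits the weight of the point but does not remove it, since a between-arm cost comparison is planned.

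**Conclusion.** The concern holds as a risk of unequal ascertainment in the exploratory cost comparison. It rests on the sources described for each arm and on the absence of a common-source or de-duplication rule in Statistical methods. The most likely effect is to overstate LuCApp's cost, because the extra record lies in that arm.

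The size is unknown. The contact ratios of 1.06 to 1.43 follow from assumed capture rates with equal true use. The bias vanishes if the form is complete in both arms and duplicates are removed. A reader might conclude that the plan is certain to bias the result, or that LuCApp will look some fixed percentage dearer. The documents support neither, since the capture rates, the cost mix and the form's content are not given, and differing form completion by arm could offset or reverse the effect. The primary analysis of TOI change at 12 weeks does not use these data and is unaffected.

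**What to change.** State in Resource use and in Statistical methods that:

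- The main between-arm comparison of resource use and cost uses the physician form alone, with the same items, recall period and schedule in both arms.
- The form asks about care since the last visit: calls, unscheduled visits, emergency care, admissions and medication changes. This keeps real use triggered by alerts in the comparison.
- The alert log is used only to cost delivery of LuCApp (staff time per alert), and events already on the form are removed.
- Form-plus-log totals, de-duplicated by a stated rule, are reported as a sensitivity analysis.

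The cost is a small revision of the form, if it does not already cover between-visit care, and of the SAP. Events seen only in the log leave the main comparison; the sensitivity analysis shows how much that matters. The form is best settled before data collection, because control contacts that were never recorded may not be recoverable later.

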As described above, the FACT-L v.4 contains four general and one lung cancer symptom-specific subscales. General subscales include: Physical Well-Being (PWB), Social/family Well-Being (SWB), Emotional Well-Being (EWB), and Functional Well-Being (FWB).(49) The Lung Cancer Subscale (LCS) assesses symptoms commonly reported by lung cancer patients (e.g., shortness of breath; loss of weight; tightness in chest). The Trial Outcome Index (TOI) is derived by adding scores on the PWB and FWB subscales to the LCS. Because they contain the most relevant questions about symptoms and physical functioning, the LCS and TOI were selected as the primary focus of this analysis. All FACT-L questions are rated on five-point Likert-type scales ranging from 0 (“not at all”) to 4 (“very much”). Therefore, because the seven-items PWB, FWB, and LCS subscales scores range from 0–28 for each subscale, TOI scores range from 0–84. Higher scores represent better QoL or fewer symptoms. The primary outcome is the change in the score on the TOI from baseline to 12 weeks. We estimated that with 120 patients (Figure 7), the study would have 80% power with a two-sided α of 0.05 to detect a significant between-group difference of 6 points in the change in the TOI score from baseline to 12 weeks, given a pooled standard deviation of 11.54 and change in the reference group score of 53.(50) After accounting for 30% attrition rate, the expected number of enrolled patients is 156 allocated 1:1 between LuCApp and usual care groups. This sample size will also allow the detection with 80% power with a two-sided α of 0.05 of 2-points difference in the LCS subscale, assuming

a pooled standard deviation of 4.15 and change in the reference group score of 19.3 (50) (Figure 8). The clinically meaningful changes on the TOI and LCS subscales of FACT-L were derived from Cella et al.(51)

The FACT-L questionnaire will be administered electronically (via LuCApp) or via paper in the control group at baseline, 12 weeks and 24 weeks, with an understanding that in the routine care setting, lung cancer therapies administration intervals vary between patients.

Figure 7 - Sample size estimation: 5 to 10 -point difference in change in TOI score at 12 weeks

[figure not shown]
[figure not shown]
[figure not shown]

Figure 8 - Sample size estimation: 1 to 5-point difference in change in LCS score at 12 weeks

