Assuming a constant recruitment rate of 6 patients per week (2 patients per centre) the study is planned to recruit consecutively for 26 weeks (Figure 9).

Figure 9 - Planned recruitment process

Randomization

Randomization services will be provided by AdvicePharma via a computer system using randomly permuted blocks and stratified by trial centers and therapy (i.e.

chemotherapy, immunotherapy and biological therapy). Nurses or physicians involved in the study will take care of the enrollment phase. After signature of informed consent, a randomization code will be generated electronically and assigned to the patient. During the informed consent procedure, the team will go carefully through the different aspects of the study design and will present LuCApp as well as the usual care alternative. During this phase the patient will have an opportunity to discuss her level of experience with mobile technology.

The study is nonblinded, in fact it is not possible to blind the participants when this type of intervention and these outcomes are under investigation.

Participants will remain on study until discontinuation of cancer treatment, voluntary withdrawal, study termination or death.

Statistical methods

The baseline differences between the intervention and control groups will be assessed using the chi-square (χ^2) test for binary demographic data and the independent sample t-test for continuous variables. We will summarize graphically and numerically the distributions of symptoms, outcomes as well as covariates.

For the primary quality of life endpoint, two groups t-test will be used to compare changes from baseline in FACT-L in the experimental group and the control group 12 weeks after randomization. A multivariable linear regression model, with change score as the dependent variable, adjusted for covariates will be fitted. The proportion of patients in each arm who experienced improved, unchanged, or worsened scores from baseline will be compared using χ^2 or Fisher's exact test. This analysis will be run for both any change and clinically meaningful changes for specific subscales (51). The analyses will be repeated at 24 weeks after randomization.

For all other questionnaires, changes from baseline in the LuCApp group and the control group at 12 and 24 weeks after randomization will be computed using t-test comparison. The SCNS-SF34, usability and ZBI data results will be summarized graphically and numerically.

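### The 80% power for change in TOI is unverified: the reference 'changes' of 53 and 19.3 look like mean scores, so the SDs beside them are probably SDs of a score, not of a change

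*Combined protocol and SAP*

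**What the plan says.** The Sample size section defines the endpoint: "The primary outcome is the change in the score on the TOI from baseline to 12 weeks". TOI is the sum of three subscales scored 0 to 28, so it runs from 0 to 84. The section then states: "We estimated that with 120 patients (Figure 7), the study would have 80% power", at two-sided 5%, for a 6-point difference between the arms in that change. The inputs behind this claim are worded as follows: "given a pooled standard deviation of 11.54 and change in the reference group score of 53". For the Lung Cancer Subscale (LCS, 0 to 28) it claims 80% power for a 2-point difference, assuming "a pooled standard deviation of 4.15 and change in the reference group score of 19.3". Both pairs of inputs are attributed to one cited trial. Enrolment is set at 156 to allow for 30% attrition.

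Under Statistical methods, the primary comparison is unadjusted: "two groups t-test will be used to compare changes from baseline in FACT-L in the experimental group and the control group" at 12 weeks. A multivariable linear regression on the change score is also planned, but its covariates are not named. The Randomization section stratifies by centre and therapy.

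The text does not say whether 11.54 and 4.15 are SDs of a score or of a change, and it gives no correlation between baseline and week 12.

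**The concern.** The figures of 53 and 19.3 are called changes in the reference group. The differences the plan treats as clinically meaningful are 6 points on TOI and 2 on LCS, so usual care would have to change by about nine times the first (53/6 = 8.8) and nearly ten times the second (19.3/2 = 9.7). As mean scores, both figures are unremarkable.

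The reference mean does not enter the sample-size formula, so the label alone changes nothing. The SD does enter it. If the means are scores, the SDs printed in the same clauses are probably SDs of scores too. The planned test needs the SD of a change, which can be larger or smaller. What is at stake is whether the stated power belongs to the stated primary analysis.

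**Working it through.** **Inputs from the Sample size section.** TOI: difference 6, SD 11.54, 120 evaluable (60 per arm). LCS: difference 2, SD 4.15. Two-sided α 0.05, power 80%, 1:1 allocation. **Assumed, because the documents give no value:** r, the correlation between baseline and 12-week scores, taken from 0.2 to 0.7.

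**Step 1. Reproduce the plan's figure.** For a two-sample t-test with difference 6 and SD 11.54, the exact t calculation needs 59.05 per arm, so 60 per arm and 120 in total. The normal approximation gives 59 per arm, 118 in total. Power at 60 per arm is 80.6% (exact t). The stated 120 follows from the stated inputs, and 53 plays no part.

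**Step 2. Can 53 and 19.3 be changes?** A mean rise of 53 needs a mean baseline of at most 84 − 53 = 31; a mean fall of 53 needs at least 53. For LCS, a rise of 19.3 needs a baseline of at most 28 − 19.3 = 8.7; a fall needs at least 19.3. Either is arithmetically possible, but neither is believable for a usual-care arm.

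**Step 3. Consequence for TOI if 11.54 is the SD of a score, equal at both visits.**

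- SD of change = 11.54 × √(2(1 − r)). For example, at r = 0.3: 11.54 × √1.4 = 13.65.
- ANCOVA residual SD = 11.54 × √(1 − r²). For example, at r = 0.3: 11.54 × √0.91 = 11.01.

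Power is from the exact t-test, 60 per arm, 6 points:

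| r | SD of change | Power, t-test on change | Evaluable N for 80% | ANCOVA residual SD | Power, ANCOVA |
|---|---|---|---|---|---|
| 0.2 | 14.60 | 61% | 188 | 11.31 | 82% |
| 0.3 | 13.65 | 67% | 166 | 11.01 | 84% |
| 0.4 | 12.64 | 73% | 142 | 10.58 | 87% |
| 0.5 | 11.54 | 81% | 120 | 9.99 | 90% |
| 0.7 | 8.94 | 95% | 72 | 8.24 | 98% |

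The two SDs coincide at r = 0.5. The t-test on change reaches 80% from r of about 0.49.

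**Step 4. Limits of the ANCOVA figures.**

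- LCS, 2 points, SD 4.15, 60 per arm: ANCOVA power is 76% at r = 0.2 and 78% at r = 0.3, and it reaches 80% at r of about 0.36. With 4.15 used as stated, the plain t-test has 74%.
- Attrition: 156 × 0.70 = 109.2, about 109 evaluable or 54 to 55 per arm. ANCOVA power for TOI is then 78% at r = 0.2.

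**The case against.** A reader might infer that 11.54 and 4.15 are established as score SDs and that the 80% power is wrong. The documents support neither. The text says only that the SDs are pooled, and the cited trial is not available here. Figures 7 and 8, whose captions refer to a difference in change, are not shown and may carry the inputs. A mislabelled mean does not prove that the SD beside it is of the same kind. Even if 11.54 is a score SD, power holds from r of about 0.49 and exceeds 80% above that. The documents give no basis for expecting r below 0.5. This part of the objection stands, and the conclusion is limited accordingly.

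A reader might also infer that ANCOVA guarantees 80% throughout. It does so only for TOI with a full 120 evaluable; step 4 shows where it falls short.

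It can also be said that the plan already has an adjusted model. If baseline TOI were among its covariates, regression on change would give the same treatment estimate as ANCOVA of the 12-week score. The plan also lists mixed-effects models among its further analyses. But baseline TOI is not named as a covariate, and the primary comparison is the unadjusted t-test, so this does not close the gap.

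Lastly, a t-test on change is valid in a randomized trial, and this trial calls itself a feasibility study and a pilot. That lowers the stakes, but the plan still makes a formal power claim, and that claim should match its test.

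**Conclusion.** The labels on 53 and 19.3 need correcting: both are credible only as mean scores. The accompanying SDs are probably SDs of a score, which is an inference and not something the plan states. Until the sponsor gives the SD of change, or r, the 80% power is unverified for the planned t-test on change. If 11.54 is a score SD, equal at both visits, power with 60 evaluable per arm runs from 61% at r = 0.2 to 95% at r = 0.7. If it is already the SD of a change, the stated 120 stands and one sentence settles the power question. In either case, adjusting for baseline TOI and the two stratification factors is a nearly free gain in precision.

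**What to change.** 1. In the Sample size section, relabel 53 and 19.3 as reference-group scores, and state whether 11.54 and 4.15 are SDs of a score or of a change.
2. Under Statistical methods, make the primary analysis an ANCOVA of 12-week TOI on arm, baseline TOI, centre and therapy. Equivalently, name those covariates in the planned change-score regression and make that model primary. Keep the unadjusted t-test as supportive.
3. State power over r = 0.2 to 0.7, at 120 evaluable and at the roughly 109 left after 30% attrition from 156. Report LCS separately, without carrying over the TOI figures.

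The cost is a small but real change to the primary analysis text, best made before any outcome data are examined. Baseline FACT-L, centre and therapy are already recorded, so no new data are needed.
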